### **13.3 Informed Consent Process**

#### **13.3.1Consent/Accent and other Informational Documents Provided to Participants**

Consent forms describing in detail the study agent, study procedures, and risks are given to the participant and written documentation of informed consent is required prior to enrolment in the trial and before any study related procedure takes place.

### **13.3.2 Consent Procedures and Documentation**

Informed consent is a process that is initiated prior to the individual's agreeing to participate in the study and continues throughout the individual's study participation. Extensive discussion of risks and possible benefits of participation will be provided to the participants and their families. Consent forms will be IRB/EC-approved and the participant will be asked to read and review the document. The investigator will explain the research study to the participant and answer any questions that may arise. All participants will receive a verbal explanation in terms suited to their comprehension of the purposes, procedures, and potential risks of the study and of their rights as research participants. Participants will have the opportunity to carefully review the written consent form and ask questions prior to signing. The participants should have the opportunity to discuss the study with their surrogates or think about it prior to agreeing to participate. The participant will sign the informed consent document prior to any procedures being done specifically for the study. The participants may withdraw consent at any time throughout the course of the trial. A copy of the informed consent document will be given to the participants for their records. The rights and welfare of the participants will be protected by emphasizing to them that the quality of their medical care will not be adversely affected if they decline to participate in this study.

### **13.4 Participant and data Confidentiality**

Participant confidentiality is strictly held in trust by the participating investigators, their staff, and the sponsor and their representatives. This confidentiality is extended to cover testing of biological samples and genetic tests in addition to the clinical information relating to participants. Therefore, the study protocol, documentation, data, and all other information generated will be held in strict confidence. No information concerning the study or the data will be released to any unauthorized third party without prior written approval of the sponsor.

The study monitor, other authorized representatives of the sponsor, representatives of the IRB/EC or pharmaceutical company supplying study product(s) may inspect all documents and records required to be maintained by the investigator, including but not limited to, medical records (office, clinic, or hospital) and pharmacy records for the participants in this study. The clinical study site will permit access to such records.

The study participant's contact information will be securely stored at each clinical site for internal use during the study. At the end of the study, all records will continue to be kept in a secure location for as long a period as dictated by local IRB/EC and Institutional regulations.

Study participant research data, which is for purposes of statistical analysis and scientific reporting, will not include the participant's contact details or identifying information. Rather, individual participants and their research data will be identified by a unique study identification number. The study data entry and study management systems used by clinical sites will be secured and password protected.

### **13.5 Insurance**

Prior to the start of the trial, the sponsor will ensure that adequate insurance for patients is in place covering losses due to death or injury resulting from the trial, in accordance with applicable laws and regulations in each country where the trial is conducted. In addition, the sponsor will ensure that adequate insurance is in place for both investigator(s) and sponsor to cover liability pertaining to death or injury resulting from the trial. The Investigator(s) will remain responsible towards the sponsor of any fault or misconduct regarding the performance of the Study.

## 14. Data Handling and Record Keeping

### 14.1 Data Collection and Management Responsibilities

- Data collection

Designated investigator staff will enter the data required by the protocol into the eCRF using fully validated software that conforms to 21 CFR Part 11 requirements. Designated investigator site staff will not be given access to the Electronic Data Capture (EDC) system until they are trained.

Web-based software will be used and no installation procedure is needed. Each site will be authorized by the Administrator to access the eCRF. Each site-qualified personnel will be allowed to access the eCRF by means of a 'login mask' requiring User ID and Password and may read, modify and update only the information he/she previously reported. Each page reports site code and patient code.

On-line validation programs will check for data discrepancies and, by generating appropriate error messages, allow the data to be confirmed or corrected before transfer to the CRO working on behalf of the Sponsor. The Investigator will certify that the data entered into the eCRF is complete and accurate.

After database lock, the investigator will receive a CD-ROM of patient data for archiving at the investigational site.

- Database management and quality control

The CRO working on behalf of the Sponsor will review the data entered into the eCRF by investigational staff for completeness and accuracy and instruct site personnel to make any necessary corrections or additions. The Data Manager will perform the cleaning session by reviewing the warning messages raised by on-line checks and by running post-entry checks by means of validation programs and data listings specific for the study. If clarifications are needed, the Data Manager will raise queries by means of data query forms through the web application. Designated investigator site staff will be required to respond to queries and the Data Manager will make the correction to the database according to the responses.

Data collection and query flows as well as the on-line and off-line checks are detailed in the Data Management Plan and Data Validation documents.

Concomitant medications and prior medications entered into the database will be coded using the World Health Organization (WHO) Drug Reference List, which employs the Anatomical Therapeutic Chemical (ATC) classification system. Medical history/current medical conditions and adverse events will be coded using the Medical dictionary for regulatory activities (MedDRA).

Data about the study drug are tracked using the eCRF. The system is supplied by CRO, who also manages the database.

The occurrence of any protocol deviations will be checked and the database will be locked and made available for data analysis after these actions have been completed and the database has been declared complete and accurate.

### 14.2 Study Records Retention

The investigator/institution should maintain the trial documents as specified in Essential Documents for the Conduct of a Clinical Trial (ICH E6 Section 8) and as required by applicable regulations and/or

guidelines. The investigator/institution should take measures to prevent accidental or premature destruction of these documents.

Essential documents (written and electronic) should be retained for a period of not less than twenty five (25) years from the completion of the study unless the Sponsor provides written permission to dispose of them or, requires their retention for an additional period of time because of applicable laws, regulations and/or guidelines. The subjects' medical files will be archived in accordance with the national laws.

### **14.3 Protocol Deviations**

A protocol deviation is any noncompliance with the clinical trial protocol or GCP requirements. The noncompliance may be on the part of the participant, the investigator, or the study site staff. As a result of deviations, corrective actions are to be developed by the site and implemented promptly.

These practices are consistent with ICH E6:

- 4.5 Compliance with Protocol, sections 4.5.1, 4.5.2, and 4.5.3
- 5.1 Quality Assurance and Quality Control, section 5.1.1
- 5.20 Noncompliance, sections 5.20.1, and 5.20.2.

It is the responsibility of the site to use continuous vigilance to identify and report deviations. All deviations must be addressed in study source documents.

### **14.4 Publication and Data Sharing Policy**

This study will ensure that the public has access to the published results of the research.

The International Committee of Medical Journal Editors (ICMJE) member journals have adopted a clinical trials registration policy as a condition for publication. The ICMJE defines a clinical trial as any research project that prospectively assigns human subjects to intervention or concurrent comparison or control groups to study the cause-and-effect relationship between a medical intervention and a health outcome. Medical interventions include drugs, surgical procedures, devices, behavioral treatments, process-of-care changes, and the like. Health outcomes include any biomedical or health-related measures obtained in patients or participants, including pharmacokinetic measures and adverse events. The ICMJE policy requires that all clinical trials be registered in a public trials registry such as ClinicalTrials.gov, which is sponsored by the National Library of Medicine. Other biomedical journals are considering adopting similar policies.

### **14.5 End of study report**

The sponsor will notify the accredited Ethics Committee and the Competent Authority for the end of study within a period of 90 days. The end of the study is defined as the last patient's last visit. In case the study is ended prematurely, the sponsor will notify the accredited Ethics Committee and the Competent Authority within 15 days, including the reasons for the premature termination.

The sponsor will submit the clinical study report with the final results of the study to the accredited Ethics Committee and the Competent Authority within one year after the end of study.

## **15. Study Administration**

### **15.1 Study Leadership**

The Scientific Committee will govern the conduct of the study and will be composed of the Sponsor Representative, the Co-ordinating Investigator and the Scientific Co-ordinating Investigator. The Scientific Committee will meet in person at least annually.

## **16. Conflict of Interest (COI) Policy**

The independence of this study from any actual or perceived influence, such as by the pharmaceutical industry, is critical. Therefore, any actual conflict of interest of persons who have a role in the design, conduct, analysis, publication, or any aspect of this trial will be disclosed and managed. Furthermore, persons who have a perceived conflict of interest will be required to have such conflicts managed in a way that is appropriate to their participation in the trial. The study leadership has established policies and procedures for all study group members to disclose all conflicts of interest and will establish a mechanism for the management of all reported dualities of interest. Financial disclosures shall be provided by study personnel who are directly involved in the treatment or evaluation of patients at the site - prior to study start.

## APPENDIX

### Appendix 1 – Preparation of Daratumumab

This medicinal product is for single-use only.

Prepare the solution for infusion using aseptic technique as follows:

- Calculate the dose (mg), total volume (mL) of DARZALEX solution required and the number of DARZALEX vials needed based on patient weight.
- Check that the DARZALEX solution is colorless to yellow. Do not use if opaque particles, discolouration or other foreign particles are present.
- Using aseptic technique, remove a volume of 0.9% Sodium Chloride from the infusion bag/container that is equal to the required volume of DARZALEX solution.
- Withdraw the necessary amount of DARZALEX solution and dilute to the appropriate volume by adding to an infusion bag/container containing 0.9% Sodium Chloride. Infusion bags/containers must be made of polyvinylchloride (PVC), polypropylene (PP), 13 polyethylene (PE) or polyolefin blend (PP+PE). Dilute under appropriate aseptic conditions. Discard any unused portion left in the vial.
- Gently invert the bag/container to mix the solution. Do not shake.
- Visually inspect parenteral medicinal products for particulate matter and discolouration prior to administration. The diluted solution may develop very small, translucent to white proteinaceous particles, as daratumumab is a protein. Do not use if visibly opaque particles, discolouration or foreign particles are observed.
- Since DARZALEX does not contain a preservative, diluted solutions should be administered within 15 hours (including infusion time) at room temperature (15°C - 25°C) and in room light.
- If not used immediately, the diluted solution can be stored prior to administration for up to 24 hours at refrigerated conditions (2°C - 8°C) and protected from light. Do not freeze.
- Administer the diluted solution by intravenous infusion using an infusion set fitted with a flow regulator and with an in-line, sterile, non-pyrogenic, low protein-binding polyethersulfone (PES) filter (pore size 0.22 or 0.2 micrometer). Polyurethane (PU), polybutadiene (PBD), PVC, PP or PE administration sets must be used.
- Do not infuse DARZALEX concomitantly in the same intravenous line with other agents.
- Do not store any unused portion of the infusion solution for reuse. Any unused product or waste material should be disposed of in accordance with local requirements.

## Appendix 2 – Guidelines for Administrating Daratumumab

Following dilution, daratumumab infusion should be intravenously administered at the appropriate initial infusion rate, as presented in the table below. Incremental escalation of the infusion rate should be considered only if the previous infusion of daratumumab was well tolerated.

### Infusion rates for daratumumab

	Dilution volume	Initial infusion rate (first hour)	Increments of infusion rate a	Maximum infusion rate
First infusion	1,000mL	50 mL/hour	50 mL/hour every hour	200 mL/hour
Second infusion b	500 mL	50 mL/hour	50 mL/hour every hour	200 mL/hour
Subsequent infusions c	500 mL	100 mL/hour	50 mL/hour every hour	200 mL/hour

a Incremental escalation of the infusion rate should be considered only in the absence of infusion reactions.

b A dilution volume of 500 mL should be used only if there were no  $\geq$  Grade 1 IRRs during the first 3 hours of the first infusion. Otherwise, continue to use a dilution volume of 1000 mL and instructions for the first infusion.

c A modified initial rate for subsequent infusions (i.e. third infusion onwards) should only be used only if there were no  $\geq$  Grade 1 IRRs during a final infusion rate of  $\geq$  100 mL/hr in the first two infusions. Otherwise, use instructions for the second infusion.

### Management of infusion-related reactions

Pre-infusion medications should be administered to reduce the risk of infusion-related reactions (IRRs) prior to treatment with DARZALEX.

For IRRs of any grade/severity, immediately interrupt the DARZALEX infusion and manage symptoms.

Management of IRRs may further require reduction in the rate of infusion, or treatment discontinuation of DARZALEX as outlined below.

- Grade 1-2 (mild to moderate): Once the patient's condition is stable, the infusion should be resumed at no more than half the rate at which the IRR occurred. If the patient does not experience any further IRR symptoms, infusion rate escalation may be resumed at increments and intervals as clinically appropriate up to a maximum rate of 200 mL/hour (Table above).
- Grade 3 (severe): If the intensity of the IRR decreases to Grade 2 or lower, restarting of the infusion may be considered at no more than half the rate at which the reaction occurred. If the patient does not experience additional symptoms, infusion rate escalation may be resumed at increments and intervals as appropriate (Table above). The procedure above should be repeated in the event of recurrence of Grade 3 symptoms. Permanently discontinue DARZALEX if the patient experiences a  $\geq$  Grade 3 infusion-related symptom at the subsequent infusion.
- Grade 4 (life threatening): Permanently discontinue DARZALEX treatment.

### Recommended concomitant medications

#### Pre-infusion medication

Pre-infusion medications should be administered to reduce the risk of IRRs to all patients approximately 1-3 hour prior to every infusion of DARZALEX as follows:

- intravenous corticosteroid (dexamethasone 20 mg, methylprednisolone 100 mg, or equivalent dose of an intermediate-acting or long-acting corticosteroid) plus
- oral antipyretics (paracetamol 650 to 1,000 mg), plus
- oral or intravenous antihistamine (diphenhydramine 25 to 50 mg or equivalent).

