### Dexamethasone

The recommended dose of dexamethasone is 40 mg (20 mg for patients > 75 years of age) orally once daily on Days 1, 8, 15 and 22 of each 28-day treatment cycle. On the days that dexamethasone dosing is concurrent with the daratumumab administration, dexamethasone will be administered at a dose of 40 mg IV or PO prior to the daratumumab infusion (IV: approximately 1 hour before, PO: 1-3 hours before) and will serve as both the pre-medication and the therapeutic dose (i.e. no other corticosteroids can be administered as pre-medication on the days that dexamethasone dosing is concurrent).

See the Summary of Product Characteristics for more details about dexamethasone.

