### **Interruption of Missed Doses**

A daratumumab dose held for more than 3 days from the per-protocol administration date for any reason other than toxicities suspected to be related to daratumumab should be brought to the attention of the sponsor at the earliest possible time. Subjects missing  $\geq 3$  consecutive planned doses of daratumumab

for reasons other than toxicity should be withdrawn from treatment, unless, upon consultation with the sponsor and the review of safety and efficacy, continuation is agreed upon.

➤ Dexamethasone

Instructions for dose modifications of dexamethasone are shown in the table below:

Dyspepsia = Grade 1-2	Maintain dose and treat with histamine (H2) blockers or equivalent. Decrease by one dose level if symptoms persist.
Dyspepsia $\geq$ 3	Interrupt dose until symptoms are controlled. Add H2 blocker or equivalent and decrease one dose level when dose restarted.
Edema $\geq$ Grade 3	Use diuretics as needed and decrease dose by one dose level.
Confusion or mood alteration $\geq$ Grade 2	Interrupt dose until symptoms resolve. When dose restarted decrease dose by one dose level.
Muscle weakness $\geq$ Grade 2	Interrupt dose until muscle weakness $\leq$ Grade 1. Restart with dose decreased by one level.
Hyperglycemia $\geq$ Grade 3	Decrease dose by one dose level. Treat with insulin or oral hypoglycemic agents as needed
Acute pancreatitis	Discontinue patient from dexamethasone treatment regimen.
Other $\geq$ Grade 3 dexamethasone-related adverse events	Stop dexamethasone dosing until adverse event resolves to $\leq$ Grade 2. Resume with dose reduced by one level.

Dexamethasone dose reduction levels:

Dose reduction levels ( $\leq$  75 years of age): Starting dose 40 mg; dose level -1 20 mg; dose level-2 10 mg on Days 1, 8, 15 and 22 of each 28-day treatment cycle.

Dose reduction levels ( $>$  75 years of age): Starting dose 20 mg; dose level -1 12 mg; dose level-2 8 mg on Days 1, 8, 15 and 22 of each 28-day treatment cycle.

If recovery from toxicities is prolonged beyond 14 days, then the dose of dexamethasone will be decreased by one dose level.

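### Section 6.1.4 fixes dexamethasone at 40 mg on infusion days, twice the stated dose for patients over 75, and the Appendix 2 steroid bullet has no exception for the same rule

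*Protocol*

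**What the plan says.** **Section 6.1.4, Dexamethasone.** The paragraph opens with an age-based dose for Days 1, 8, 15 and 22 of every cycle: "The recommended dose of dexamethasone is 40 mg (20 mg for patients > 75 years of age) orally once daily". For days that coincide with an infusion it then says "dexamethasone will be administered at a dose of 40 mg IV or PO prior to the daratumumab infusion". That dose "will serve as both the pre-medication and the therapeutic dose", and "no other corticosteroids can be administered as pre-medication on the days that dexamethasone dosing is concurrent". This second rule mentions neither age nor a reduced dose level.

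**Elsewhere on the dose.** The Protocol Summary (Description of Study Treatment), Section 4.1 and the Table 7.2 treatment rows all give 40 mg, or 20 mg over 75. Section 4.1 states it as a weekly total. Section 6.1.5 sets the toxicity reductions for patients aged 75 or under as "Starting dose 40 mg; dose level -1 20 mg; dose level-2 10 mg". For patients over 75 the levels are 20, 12 and 8 mg.

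**Appendix 2, Pre-infusion medication.** Under the heading "Recommended concomitant medications", pre-medication is to be given "to all patients approximately 1-3 hour prior to every infusion of DARZALEX". The steroid item is an "intravenous corticosteroid (dexamethasone 20 mg, methylprednisolone 100 mg, or equivalent dose of an intermediate-acting or long-acting corticosteroid) plus" an oral antipyretic and an antihistamine. It makes no reference to Section 6.1.4 and states no exception.

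**Pointers.** The daratumumab part of Section 6.1.4 and Section 7.3.1 refer sites to Appendix 2. Section 7.3.2 refers to Section 6 and Appendix 2 together, without ranking them.

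**The concern.** Dexamethasone is one of the two study drugs, so the dose intended on an infusion day should be readable from a single place. There are two faults.

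The main one is inside Section 6.1.4. Consecutive sentences give a patient over 75 either 20 mg or 40 mg on the same day. The 40 mg is worded as what will be given, the 20 mg as a recommendation. A site that takes the concurrent-day sentence as the specific instruction for infusion days would give 40 mg to the group for whom the protocol halves the dose. The sentence also does not refer to the reduced levels in Section 6.1.5.

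The secondary one is in Appendix 2. A site working from that page would give 20 mg dexamethasone, or another agent altogether, where Section 6.1.4 requires study dexamethasone alone.

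The faults are linked. Pointing Appendix 2 to Section 6.1.4 without correcting the 40 mg would lead more sites to the wrong dose for patients over 75.

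A smaller consequence concerns reporting. Protocol Section 10.4.6 and SAP Section 6.6.1.6 plan relative dose intensity for each component, which needs one agreed planned dose per day.

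**Working it through.** The plan states no figure to reproduce. The check is an overlay of the two schedules followed by a comparison of doses.

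**Step 1: which days coincide** (Section 6.1.4, Table 7.2).

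| Cycles | Daratumumab days | Dexamethasone days | Infusions | On a dexamethasone day |
|---|---|---|---|---|
| 1–2 | 1, 8, 15, 22 | 1, 8, 15, 22 | 2 × 4 = 8 | 8 |
| 3–6 | 1, 15 | 1, 8, 15, 22 | 4 × 2 = 8 | 8 |
| 7 onward | 1 | 1, 8, 15, 22 | 1 per cycle | 1 per cycle |

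All 8 + 8 = 16 scheduled infusions in cycles 1–6 coincide with dexamethasone, and so does every later one. In cycles 1–2 all 8 dexamethasone days are also infusion days. The concurrent-day rule is therefore the rule for every scheduled infusion while dexamethasone is being given.

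**Step 2: the concurrent-day dose against the stated starting dose.**

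- Aged 75 or under: 40/40 = 1. No conflict.
- Over 75: 40/20 = 2.
- Over 75, cycles 1–2: dexamethasone days on which 20 mg would be given under the literal rule = 8 − 8 = 0.
- Section 4.1 puts the weekly total over 75 at 20 mg. One 40 mg infusion-day dose already exceeds that by 20 mg.

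**Step 3: Appendix 2 against Section 6.1.4 on a coinciding day, patient aged 75 or under at the starting dose.**

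| Feature | Appendix 2 | Section 6.1.4 |
|---|---|---|
| Dexamethasone dose | 20 mg | 40 mg |
| Other agent | methylprednisolone 100 mg or equivalent allowed | none allowed as pre-medication |
| Route | IV | IV or oral |
| Timing | about 1–3 hours before | IV about 1 hour, oral 1–3 hours before |

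Dose conflicts (20/40 = 0.5), and so does agent if methylprednisolone is chosen. Route and timing do not conflict, because an IV dose about one hour before the infusion satisfies both texts.

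**Step 4: is the Appendix 2 bullet ever needed?** Yes. Section 6.1.5 interrupts dexamethasone for Grade 2 confusion, mood alteration or muscle weakness, whereas the non-hematologic criterion for holding daratumumab starts at Grade 3. Infusion days without study dexamethasone can therefore occur, and the bullet should be given an exception, not deleted.

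**The case against.** **The two texts can be reconciled.** Section 6.1.4 is specific and exclusive, and Appendix 2 sits under a heading that calls its contents recommended. A general recommendation with a specific exception is a coherent reading. Section 7.3.2 also cites Section 6, and the daratumumab pointer is in Section 6.1.4 itself, just above the dexamethasone rule. Only Section 7.3.1 bypasses it. This stands, and it is why the Appendix 2 fault is secondary: what is missing there is an exception and a reference back.

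**The amendment log does not settle precedence.** Used only as a guide to intent, the Amendment 1 log shows that the concurrent-day phrase in Section 6.1.4 and the 20 mg dexamethasone in Appendix 2 were added together, the latter to reconcile the appendix with study procedures. Both were deliberate, so the log favours neither.

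**Larger multiples.** A reader might infer that patients at reduced levels would receive far too much: 40/20 = 2 and 40/10 = 4 for those aged 75 or under, 40/12 = 3.3 and 40/8 = 5 for those over 75. The documents do not support this as an expected result. Section 6.1.5 sets the reduced doses for Days 1, 8, 15 and 22, which include every scheduled infusion day, so a site would have to ignore it. The supportable point is that Section 6.1.4 does not refer to those levels.

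**Added doses.** A reader might also infer 40 + 20 = 60 mg from giving both steroids. Section 6.1.4 expressly bars that.

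**The dose is only recommended.** The Protocol Summary and Section 4.1 leave dexamethasone to standard practice. That makes the age-based dose flexible, but the concurrent-day 40 mg is not worded as a recommendation, so the inconsistency remains.

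**Conclusion.** The concern holds in two parts. The main defect is the flat 40 mg in Section 6.1.4, which is 2 times the stated starting dose for patients over 75 and does not carry through the Section 6.1.5 levels. The secondary defect is the absence from Appendix 2 of any exception for coinciding days.

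This assumes that 20 mg is the intended infusion-day dose for patients over 75. The Protocol Summary, Section 4.1, Table 7.2 and the first sentence of the same paragraph support that, and nothing in the protocol says that infusion days should differ by age group.

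The size is per infusion day and conditional on a literal reading. How often sites would read it that way is unknown, so no cumulative excess is claimed. Nor should a reader infer an effect on progression-free survival, sample size or power, since the documents give no basis for one.

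Whether patients assigned 8, 10 or 12 mg need a minimum pre-medication dose, given that Appendix 2 lists 20 mg, is a clinical decision that the documents leave open. It is not part of this finding.

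**What to change.** Make two edits together.

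1. **Section 6.1.4, concurrent-day sentence.** Replace 40 mg with: *the patient's assigned dose (40 mg, 20 mg if over 75 years, or the current Section 6.1.5 dose level)*.
2. **Appendix 2, steroid bullet.** Add: *On days when study dexamethasone is given, that dose is the corticosteroid pre-medication (see Section 6.1.4) and no other steroid pre-medication is given. The listed IV steroid applies only on infusion days without study dexamethasone.*

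Leave the post-infusion steroid in Appendix 2 as it is; the bar in Section 6.1.4 covers pre-medication only. Do not add an automatic top-up to 20 mg for patients on 8 to 12 mg. Doses that low arise only from toxicity reductions, and a top-up could reverse them. The sponsor should decide that question separately.

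The cost is a short change to dosing text. Under Section 13.2 it needs ethics committee and/or competent authority approval, and it can be bundled with the next amendment. It requires no new data, visits or analyses.
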